3.2 Preliminary Data

We have previously demonstrated a wide breadth of CD4 repertoire to influenza, which includes up to 100 distinct peptide specificities in the primary response [6-8]. However, different populations of CD4 T cells, distinguished by their antigen specificity, may not contribute to the all functions important in development of a specific immune response. In particular, it has been demonstrated that protein vaccines and some enveloped viruses [9], delivery of help for antibody responses requires that the B cell and CD4 T cell recognize the epitopes from the

same protein antigen. In the case of influenza antibodies specific for HA and NA, CD4 T cells specific for epitopes in these proteins may be the only ones relevant for development of the antibody response. This help for high affinity Ab production may be primarily provided by cells belonging to the Tfh lineage (reviewed in [10]). However, most studies of the cellular immune response to influenza vaccine have not separately tracked the specific CD4 cells with these combined properties, leaving the contribution of these cells undetected. In contrast, monitoring CD4 T cells that do not have these specificities or function will likely contribute noise to the assessment of CD4 help for Ab responses to influenza.

In the first full year of this study, we found that there were unexpected differences in the serum antibody responses to vaccination between the study groups. In particular, serum HAI antibody responses to the baculovirus-expressed HA were more frequent and the mean fold rise was greater than those to the egg-grown vaccine, possibly consistent with the hypothesis that a more directed CD4 T cell response is more effective at providing help for antibody.

[figure not shown]

Interpretation of these results is complicated by the fact that the dosage level of the rHA vaccine was approximately 3 times that of the egg or cell culture vaccines, so that the more vigorous antibody responses may simply be dose related rather than reflective of CD4 specificity. Despite randomization, pre-vaccination titers were highest in the Fluzone group, as well as history of prior vaccination (18/22 in Fluzone, 16/22 in Flublok, and 13/26 in Flucelvax). In addition, we were unable to find significant numbers of subjects with pre-vaccination serum antibody titers of $\leq 1:8$ to the pH1N1 component of the vaccines.

For these reasons, we modified our protocol by :

1. Adding the high dose influenza vaccine (Fluzone HD). This may allow separation of the effects of dose from the effects of vaccine composition
2. Eliminating screening for low titers of antibody to pH1N1 and instead stratifying randomization based on history of prior vaccination
3. Continuing to encourage re-enrollment in subsequent years with assignment to the same group, in order to assess the effect of vaccine composition on the response to revaccination.

Secondly, in the 2017-2018 we noted that the Flucelvax H3 component was as poorly immunogenic as that of Fluzone SD despite the differences in manufacturing (cell-based derivation versus egg-based). Post-vaccination antibody titers in Flucelvax recipients were low to all H3N2 viruses tested, including the egg-based, cell-based and two wild-type H3N2 strains. Recent findings have demonstrated that egg adaptation of vaccine viruses during vaccine development for products made in eggs has led to decreased protection against wild-type H3N2 viruses for products like Fluzone SD. However, we would have expected Flucelvax which avoids issues of egg adaptation, since vaccine viruses are grown in cell culture, to be more immunogenic to wild-type H3N2 strains. The reason for our findings of poor immunogenicity of the Flucelvax H3 components which was similar to egg-based Fluzone SD remains unclear and further study is needed outside the scope of the current project.

For this reason, though we have now chosen to eliminate the Flucelvax arm of the study for newly enrolled subjects. However, to preserve the ability to assess the secondary aim of the effect of repeated vaccination without introducing confounders, subjects who have received 2 or more consecutive years of Flucelvax will continue to receive the same vaccine in subsequent years.

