5 STUDY DESIGN

Subjects age 18-49 years will be stratified by their prior vaccination history, followed by randomized assignment to receive one of three licensed vaccines: Fluzone SD, Fluzone HD and Flublok. Block randomization will be performed separately for the two groups. Study subjects who participated in a previous year can be re-enrolled and receive the same vaccine as previously (Fluzone SD, Fluzone HD, Flublok, Flucelvax). Because the goal of the protocol is to evaluate the immune response to the vaccine and is not intended as a formal comparison of the adverse event profile, the vaccine assignment is not blinded. Following vaccination, subjects will have blood sample obtained at the time points illustrated above. The last study visit will take place 6 months after vaccination.

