7 STUDY INTERVENTION/INVESTIGATIONAL PRODUCT

7.1 Study Product Description

Fluzone Standard Dose (Sanofi Pasteur). Quadrivalent subvirion vaccine (IIV4) produced in embryonated hen's eggs and administered intramuscularly at a dose of 15 ug of HA (as determined by SRID) per component.

Fluzone High Dose (Sanofi Pasteur). Trivalent subvirion vaccine (IIV3) produced in embryonated hen's eggs and administered intramuscularly at a dose of 60 ug of HA (as determined by SRID) per component.

FluCeIVax (Novartis). Quadrivalent subunit vaccine produced in MDCK mammalian cell culture (ccIV4) administered intramuscularly at a dose of 15 ug of HA (determined by SRID) per component

FluBlok (Protein Sciences) Quadrivalent purified recombinant hemagglutinin vaccine (rIV4) produced in insect cells and administered intramuscularly at a dose of 45 ug of HA (determined by SRID) per component.

All four products are indicated for the prevention of influenza in adults, although Fluzone HD is only indicated for prevention in adults ages 65 and older.

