12.4 Final Analysis Plan

We will define the groups as: G1 (egg derived vaccine) = G1a (seronegative to pH1N1 virus and receiving egg derived vaccine) + G1b (seropositive and receiving egg derived vaccine); G2 (baculovirus derived vaccine) = G2a (seronegative to to pH1N1 virus and receiving baculovirus derived vaccine) + G2b (seropositive and receiving baculovirus derived vaccine). The log transformation will be applied to stabilize variance, as suggested by our past experience [18]. The between-group and among-group comparison in each of the outcomes will be based on both standard statistical analysis approaches using summary statistics and the complicated random variance model approach. Specifically, each of CD4 specific cells for different Influenza proteins (eg HA, NP etc), memory B cell derived polyclonal antibodies, HAI and MN titers among the four groups and between G1 and G2, between G1a and G2a, and between G1b and G2b, we will use maximum responses or maximum boost responses (maximum value after day 0 – value at day 0) or maximum fold increase as endpoint and do group comparison by ANOVA for among-group comparison and two-sample t-test for between-group comparison, or their nonparametric analogy of Kruskal-Wallis test and Wilcoxon Rank sum test, respectively, may also be applied for robustness. Multiple comparisons may subject to Bonferroni correction, if appropriate. Correlation test such as Pearson correlation analysis, or its nonparametric analogy of Spearman correlation analysis, will be used to study how baseline CD4 responses and/or memory B cell derived polyclonal antibodies, HAI, MN titers affect the boost responses of CD4, memory B cell derived polyclonal antibodies, HAI and MN titers after vaccination.

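### Fluzone HD was added to help separate dose from composition, but section 12.4 never says how HD will be used, so an egg-versus-recombinant difference cannot be attributed to composition

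*Combined protocol and SAP*

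**What the plan says.** Section 3.2 reports more frequent and larger HAI responses to Flublok than to the egg vaccine in the first full year. It then cautions that "the dosage level of the rHA vaccine was approximately 3 times that of the egg or cell culture vaccines", and concludes that dose alone, not CD4 specificity, could account for the stronger responses. The first of the protocol modifications that follow is to add Fluzone HD, on the ground that "This may allow separation of the effects of dose from the effects of vaccine composition".

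Section 7.1 gives the HA content per strain:

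- Fluzone SD: "administered intramuscularly at a dose of 15 ug of HA (as determined by SRID) per component"
- Fluzone HD: "administered intramuscularly at a dose of 60 ug of HA (as determined by SRID) per component" (trivalent)
- Flublok: "administered intramuscularly at a dose of 45 ug of HA (determined by SRID) per component"

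Section 5 gives newly enrolled subjects "randomized assignment to receive one of three licensed vaccines: Fluzone SD, Fluzone HD and Flublok".

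Section 12.4 defines G1 as egg-derived and G2 as baculovirus-derived, each split by pH1N1 serostatus, and plans comparisons among the four groups and "between G1 and G2, between G1a and G2a, and between G1b and G2b". HD is not mentioned. The same section plans mixed-effects models with a group indicator and possibly demographic covariates, and a regression of antibody boost on the CD4 specificities. Neither has a dose term. Sections 12.1 and 12.2 are also framed as egg versus recombinant.

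**The concern.** The sponsor identified a confounder and added an arm to address it, but the analysis plan does not use that arm for the purpose. Followed literally, 12.4 either pools two egg doses that differ fourfold or leaves HD's place in G1 undefined.

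The model under test (section 3.3) is that internal virion proteins in egg vaccine impair CD4 help for antibody. If more HA raises the response, Flublok against SD tends to favour that model for a reason unrelated to composition, and Flublok against HD tends to oppose it. Assignment is open label and immunogenicity is analysed yearly (section 12.3.2). Without a prespecified rule, the choice of egg comparator and the reading of a mixed result could be settled after the data are seen.

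**Working it through.** **Inputs.** HA per strain: SD 15, HD 60, Flublok 45 ug (section 7.1). From section 12.2: 45 per group, two-sided 0.05, CD4 CV 0.25 to 0.4. Assumed, because the documents give no figure: the ratio R of HD to SD response, a log-linear egg dose response, and a log2 titre SD of 1.5 to 2.

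**1. The plan's own figure.** Flublok to SD is 45/15 = 3.0, which reproduces the threefold statement in section 3.2. Flublok to HD is 45/60 = 0.75. Against SD and HD pooled 1:1, it is 45/30 = 1.5 (geometric mean dose) or 45/37.5 = 1.2 (arithmetic mean). None of these equals 1, so the problem remains whether G1 means SD, HD or both.

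**2. What dose alone would produce.** The position of 45 ug between 15 and 60 on log dose is w = ln(45/15)/ln(60/15) = ln 3/ln 4 = 0.792. With no composition effect:

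| R (assumed) | Flublok/SD = R^w | Flublok/HD = R^(w-1) | Flublok/pooled = R^(w-0.5) |
|---|---|---|---|
| 1.3 | 1.23 | 0.95 | 1.08 |
| 1.5 | 1.38 | 0.92 | 1.13 |
| 2.0 | 1.73 | 0.87 | 1.22 |

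**3. How often that would be significant, with 45 per arm.**

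- CD4, with log SD = sqrt(ln(1+CV^2)), at R = 1.3: 73-98% against SD, 10-18% against HD and 19-40% against pooled egg (45 vs 90), for CV 0.4 down to 0.25.
- Titres, Flublok against SD, log2 SD 2 down to 1.5: 19-31% at R = 1.5 and 46-70% at R = 2.
- Section 12.2 aims at CD4 differences of 10% to 20%. Dose alone gives these against SD when R = 1.10^(1/0.792) = 1.13 to 1.20^(1/0.792) = 1.26.

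**4. What the three arms can support.** The interpolated contrast is Flublok - [0.21 SD + 0.79 HD] on the log scale. Its variance factor is 1 + 0.208^2 + 0.792^2 = 1.67, against 2.00 for a pairwise comparison; sqrt(1.67/2.00) = 0.91, so the SE is about 9% smaller. At 80% power the detectable CD4 increase is 14.2% to 23.1%, against 15.7% to 25.6% pairwise.

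**5. How far the assumed shape matters.** Linear interpolation has weight (45-15)/(60-15) = 0.67. At R = 2 it moves the estimate by 2^(0.792-0.667) = 1.09-fold. The monotone extremes move it further. If the egg response at 45 ug already equals HD's, the log interpolation is off by 2^0.208 = 1.16-fold. If it still equals SD's, it is off by 2^0.792 = 1.73-fold. In those two cases the dose-adjusted contrast is simply Flublok-HD or Flublok-SD, so under monotonicity the pairwise comparisons bound the dose-adjusted ratio.

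**The case against.** The strongest reply is that the objectives compare products. The hypothesis in 12.1 is that responses differ between recipients of egg-derived and recombinant vaccines. If Flublok does better because it carries more HA, that is a true product difference, and section 3.2 already warns against reading it as CD4 specificity. This stands. A reader might take the rates in step 3 as false-positive rates of the planned tests, but the documents do not support that. They matter only if the result is then credited to composition.

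A reader might also infer that 12.4 has only two-group and omnibus tests, or that the design cannot separate dose at all. Neither is right. The mixed models could yield HD-SD and any weighted contrast if the group indicator were vaccine arm, although 12.4 defines its groups otherwise and names no such contrast. The arms also bracket Flublok: under a monotone dose response, Flublok above HD could not be due to HA dose, while Flublok between SD and HD is what dose alone predicts. That reading needs no dose-response curve, but the plan does not state it.

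Reading the four groups of 12.4 as the four vaccines would not close the gap, because an omnibus test does not separate dose from composition.

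Finally, the study calls itself explorative, says only that HD may help, and does not show 45 newly randomised subjects per arm in three-arm seasons. This limits the severity and makes step 3 illustrative.

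**Conclusion.** The point holds as a gap in the analysis plan, not as a flaw in the design. Section 12.4 does not say where HD belongs, does not separate the egg doses, and names no contrast that serves HD's stated purpose. As written, a G1-versus-G2 difference cannot be attributed to composition.

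That conclusion follows from the doses alone. Its numerical size rests on an assumed HD/SD ratio and log-linearity: at R = 1.5 to 2, dose alone accounts for a 1.38- to 1.73-fold advantage over SD, an 8% to 13% deficit against HD, and a 1.13- to 1.22-fold advantage over pooled egg.

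It is tempting to go further and make the interpolated contrast the sole test of composition. The documents do not support that. Two egg doses cannot test the curve's shape, and the worst monotone case (1.73-fold at R = 2) is as large as the bias being removed. The contrast also equalises HA dose only. Flublok differs from egg vaccine in egg-adaptation changes (footnote to the section 3.1 table), host-cell glycosylation (section 3.3) and non-HA protein content. This is a cheap, worthwhile improvement.

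**What to change.** Amend 12.4 as follows.

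- Analyse SD, HD and Flublok as separate randomised arms, not one egg group against Flublok. Use newly randomised subjects from seasons when all three arms were open, strains common to all three products (so not B Yamagata, which HD lacks), and log titre and log CD4 response.
- Prespecify HD-SD as the dose effect within egg vaccine, together with Flublok-SD and Flublok-HD. State the reading in advance: if the dose response is monotone, Flublok above HD cannot be explained by HA dose, whereas Flublok between SD and HD is compatible with dose alone.
- Add Flublok - [0.21 SD + 0.79 HD] as a supportive dose-adjusted estimate. As sensitivity analyses give linear interpolation (HD weight 0.67) and the two monotone bounds, with the egg response at 45 ug set equal to SD's or to HD's.
- State that the contrast rests on an untestable dose-response shape and adjusts for HA dose only, not egg adaptation, glycosylation or non-HA protein.

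The cost is about one paragraph of 12.4, plus a possibly smaller analysis set from the restriction to three-arm seasons. No new subjects or assays are needed, and no dose change is implied.

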3.3 Rationale

Our observations to date lead to the following model: Traditional egg-derived TIV have contaminating internal virion proteins that preferentially elicit memory CD4 T cells specific for these proteins. These CD4 T cells will have limited efficacy as helpers for the neutralizing Ab response and will suppress the CD4 T cell response to new HA epitopes in the vaccine. The current study will test this hypothesis by comparing CD4 cell responses to specific epitopes, and the subsequent B cell and antibody response, in subjects receiving a vaccine containing only HA protein to vaccines with more complex antigenic characteristics. The CD4 T cell reactivity to pools of unique, conserved, and total pH1 HA peptides as well as H3, influenza B HA, NP, and M1 peptides will be quantified using cytokine Elispot assays and flow cytometry, and then compared to the subsequent antibody and B cell response.

We will also use this study as an opportunity to evaluate the effects of prior vaccination. Recent studies have emphasized the potential negative effect of vaccination in prior years on both the immune response as well as the protective effectiveness of current vaccine. In order to evaluate this phenomenon in the context of multiple vaccine formulations, we will ascertain the prior vaccination history of the subjects and stratify vaccination based on vaccine history.

In addition, subjects who participated in this study in a previous year are eligible to re-enroll, and will receive the same vaccine that they were randomized to previously. This will allow an evaluation of differences between vaccine formulations in the responsiveness to multiple vaccinations.

Furthermore, recent studies indicate reports that the glycosylation pattern of viral hemagglutinins produced in cell culture can vary depending on the host cell used [11, 12], and that this can affect CD4 T cell immunogenicity and antibody recognition. As a cell culture-based influenza vaccine production platform offers many advantages and may eventually supplant the traditional egg-based approach, it is of great value to understand the CD4 T cell response induced by this vaccine and how this affects neutralizing Ab production.

Recent data have also suggested that the failure of seasonal influenza infection to induce substantial levels of stalk specific antibody may be due to the relatively inaccessible nature of this epitope. As part of this study, we will also compare the specificity of the human antibody response between the vaccine groups, with the hypothesis that the rHA vaccine will more readily allow targeting of these important, broadly conserved epitopes. We have compelling preliminary data demonstrating that multiple antibodies that we have isolated have a particularly slow on rate when they bind to the HA-stalk versus the HA-globular head epitopes on whole virions, but not on recombinant HA trimmers expressed in baculovirus. We hypothesize that a free, recombinant HA vaccine will allow more efficient targeting of the HA-Stalk epitopes.

3.4 Potential Risks and Benefits

3.4.1 Potential Risks

The risks and discomforts of this study include risks associated with the vaccine, the risks associated with study procedures (blood drawing and possible loss of confidentiality).

In placebo-controlled trials in adults, inactivated seasonal vaccines are associated with mild local pain at the site of administration. Although high-dose vaccine is not indicated in individuals under 65 years of age, clinical trials of such vaccines in healthy adults suggest that high dose vaccine is association with slight increases in mild local reactogenicity but are otherwise well tolerated [13]. Systemic symptoms like fever and malaise occur at rates equal to placebo.

During the swine influenza vaccine campaign of 1976, about 10 per 1,000,000 vaccine recipients in excess of the background rate developed the paralytic illness called Guillain-Barré Syndrome (GBS). In the subsequent decade, no association between seasonal influenza vaccine and GBS was found. More extensive investigations of this potential association occurring in the 1990s revealed that there was a small but detectable risk of GBS in the 6 weeks following seasonal influenza immunization: an attributable risk of approximately 1 per 1,000,000, adjusted for potential confounders. In the period since the Vaccine Adverse Event Reporting System (VAERS) was established in 1990, the rates of GBS reports following influenza vaccination have declined substantially. The annual reporting rate in that period was highest in the 1993-1994 influenza season (1.7 per 1,000,000 vaccinees) and lowest in the last season analyzed in the report, 2002-2003 (0.4 per 1,000,000 vaccinees) [14]. No cases of GBS have been reported following receipt of novel H1N1 influenza vaccines to date, but the total number of recipients is only in the thousands. Most persons who develop GBS recover completely.

Drawing blood causes transient discomfort and may cause fainting. Bruising at the blood draw site may occur but can be prevented or mitigated by applying direct pressure to the draw site for several minutes. The use of alcohol swabbing and sterile equipment will make infection less likely at the site where blood will be drawn.

Personal health information of the subjects will be collected to determine eligibility and to evaluate safety outcomes throughout the study. Research personnel will make every effort to keep this information confidential. Still, a risk of participation is that the confidentiality of this information could be lost.

3.4.2 Known Potential Benefits

All four products being used in this study are licensed vaccines for seasonal influenza and would be expected to provide some protection against influenza illness caused by the strains contained within the vaccine.

4 OBJECTIVES AND OUTCOME MEASURES

4.1 Study Objectives

Primary Objective

- Comparison of the serum antibody response to immunization with pure HA, cell-derived and egg derived subvirion vaccines in adults age 18-49 years
- Comparison of the HA- specific CD4 T cell response in adults receiving pure HA, cell-derived vaccine egg-derived split or subvirion vaccines

Secondary Objectives

- Comparison of the epitope specificity of B cells following vaccination with HA or subvirion vaccines

Evaluation of the different vaccine formulations to induce HA specific antibodies that recognize circulating viruses

Exploratory Objective

- Confirmation of the safety of the licensed vaccines in healthy adults
-
- Evaluation of the effect of repeated vaccination on the immune response

4.2 Outcome Measures

4.2.1 Primary Outcome Measures

The primary outcome measure for this study is:

- Mean change in the specificity, quantity and quality of serum antibody titers to the vaccine viruses, pH1N1, H3 and influenza B using HAI (year 1-5) and MN for pH1N1 and H3 viruses (years 1-5 from Day 0 to Day 28)

- Mean change in the CD4 T cell reactivity to pools of total pHA peptides derived from the pH1N1 HA, as well as H3, influenza B HA, NP, and M1 peptides will be quantified using cytokine Elispot From Day 0 to Day 14

4.2.2 Secondary Outcome Measures

Secondary and tertiary outcome measures are listed below:

Secondary Outcome Measures

[figure not shown]
- Antibody specificity of cloned plasmablasts from subjects in each group
-
- Correlations of CD4 T cell ELISPOT number (Day 0 to Day 14) and antibody titers (Day 0 to Day 28) in subjects from each group (year 1-3), R value per cohort will be reported

Tertiary Outcome Measure

- Vaccine related adverse events
- Mean change in the CD4 T cell reactivity to pools of total pHA peptides derived from the pH1N1 HA, as well as H3, influenza B HA, NP, and M1 peptides will be quantified using cytokine Elispot from Day 0 to Day 14 for subjects with successive years of vaccination

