Various parametric or nonparametric mixed-effects regression approaches will be used to study the dynamic curve of each outcome, to take account of the correlation among observations from the same subjects over time. Group indicator will enter the model as a predictor and thus can be compared simultaneous at each time point and also by difference from difference approach to control the effect of baseline values. Demographic information may be controlled by entering the model as predictors. To further investigate the effect of CD4 cell specificity in helping neutralizing antibody responses, regression analysis will be applied, with boost or fold increase of HAI or MN titers as responses, all the CD4 cell specificities as predictor, possibly adjusting demographic variables. Type I and III sum of squares and standard coefficient estimates can be used to compare the effect of CD4 specificities in helping neutralizing antibody responses. The parametric or nonparametric mixed-effects regression approaches may also be used to compare the effects to take account of within-subject correlation. Among-group plasmablast comparisons will be proceeded by: 1). One-way ANOVA, or its nonparametric analog of Kruskal-Wallis test; 2). Repeated ANOVA or its nonparametric analog of Friedman test for simultaneous pairwise comparison, with within-subject correlation taken into account.

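### Section 12.4 does not specify the CD4–antibody correlation listed in 4.2.2, and its regression for CD4 help leaves the CD4 timepoint open and omits baseline titre

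*Combined protocol and SAP*

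**What the plan says.** **Section 4.2.2** lists "Correlations of CD4 T cell ELISPOT number (Day 0 to Day 14) and antibody titers (Day 0 to Day 28"), to be given "in subjects from each group (year 1-3), R value per cohort will be reported". The word change does not appear. It is the likely reading, because 4.2.1 uses the same two windows for its primary outcomes and defines each as a mean change, for example "Mean change in the CD4 T cell reactivity to pools of total pHA peptides derived from the pH1N1 HA", measured from Day 0 to Day 14.

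**Section 12.4, correlation.** One sentence specifies a correlation: "Correlation test such as Pearson correlation analysis, or its nonparametric analogy of Spearman correlation analysis, will be used to study how baseline CD4 responses" and baseline antibody measures "affect the boost responses of CD4, memory B cell derived polyclonal antibodies, HAI and MN titers after vaccination". The same section defines one of its endpoint options as "maximum boost responses (maximum value after day 0 – value at day 0").

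**Section 12.4, regression.** To examine how CD4 specificity helps neutralizing antibody, the plan uses a regression "with boost or fold increase of HAI or MN titers as responses, all the CD4 cell specificities as predictor". Demographic variables are a possible adjustment. Day 0 titre and Day 0 CD4 are not mentioned there.

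**Sampling.** CD4 cells are assayed on Days 0, 3, 7, 14 and 180 (9.2.1). Serum is drawn on Days 0, 28 and 180 (8.2, 8.3.4, 8.3.6 and the table in section 19).

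**The concern.** The trial's model (3.1, 3.3) is that CD4 cells specific for HA supply the help for HA antibody. The outcome in 4.2.2 bears directly on it: does the CD4 response in the first two weeks go with the antibody response at four weeks? An analyst working from 12.4 alone would not produce that quantity. They would correlate baseline CD4 with a boost, and would have to choose the CD4 timepoint for the regression themselves.

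Two features of 12.4 make this more than a drafting gap. First, a maximum over all post-vaccination visits can pair a Day 180 CD4 value with a Day 28 titre, which reverses the time order that a help hypothesis needs. Second, 3.1 says that the antibody response is smaller in people who start with higher titres. A regression for CD4 help that leaves out the Day 0 titre can therefore mix help with prior immunity. Section 3.2 reports that pre-vaccination titres and vaccination history differed between arms in the first full year (18/22, 16/22 and 13/26 previously vaccinated), so this mixing could also differ by arm.

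**Working it through.** The plan states no expected R, sample size or power for this outcome, so there is no figure to reproduce. The check is a comparison of the text, then a calculation of how far the two correlations can differ.

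**1. The definitions side by side**

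| | 4.2.2 outcome | 12.4 correlation | 12.4 regression |
|---|---|---|---|
| CD4 variable | Day 0 to 14 | baseline | timepoint not stated |
| Antibody variable | Day 0 to 28 | boost after vaccination | boost or fold increase |
| Adjustment | none stated | none stated | demographics, possibly |
| Output | R per cohort | correlation | coefficients, sums of squares |

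Neither analysis in 12.4 yields the 4.2.2 quantity without further choices. If the Day 0 to 14 wording meant values across the window instead of a change, it would still not be baseline CD4 alone.

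**2. Which days can supply the maximum.** CD4: 3, 7, 14 or 180. Antibody: 28 or 180. Nothing ties the maximum to Day 14 or Day 28.

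**3. How different the correlations can be.** Every value here is an assumption; none comes from the documents. On the log scale let C0 and A0 be baseline CD4 and baseline titre, each with variance 1 and correlation ρ. Take loadings of 0.5 to 0.7 on prior immunity, so ρ = 0.5² to 0.7² = 0.25 to 0.49. Then

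- dC = -0.4·C0 + e1
- dA = g·dC - 0.5·A0 + k·C0 + e2

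Here g is the help slope, k is a direct effect of baseline CD4, and e1 and e2 have SD s (0.8 to 1.0). It follows that

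- Var(dC) = 0.16 + s²
- Cov(C0, dA) = -0.4g - 0.5ρ + k
- Cov(dC, dA) = g·Var(dC) + 0.2ρ - 0.4k
- Var(dA) = g²·Var(dC) + 0.25 + k² + s² + 0.4gρ - 0.8gk - kρ
- partial R of dC and dA given C0 and A0 = g/√(g² + 1)

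Two cases worked through, both with g = 0.4, s = 0.8 and Var(dC) = 0.80:

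- k = 0, ρ = 0.49: Var(dA) = 0.128 + 0.25 + 0.64 + 0.0784 = 1.0964. Baseline R = (-0.16 - 0.245)/1.047 = **-0.39**. Change R = (0.32 + 0.098)/(0.894 × 1.047) = **+0.45**.
- k = 0.4, ρ = 0.25: Var(dA) = 0.128 + 0.25 + 0.16 + 0.64 + 0.04 - 0.128 - 0.10 = 0.99. Baseline R = (-0.16 - 0.125 + 0.4)/0.995 = **+0.12**. Change R = (0.32 + 0.05 - 0.16)/(0.894 × 0.995) = **+0.24**.

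Ranges over ρ = 0.25 and 0.49, s = 0.8 and 1.0:

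| Help slope g | Direct effect k | Baseline CD4 with dA | dC with dA | Partial R |
|---|---|---|---|---|
| 0.4 | 0 | -0.39 to -0.23 | +0.39 to +0.45 | 0.37 |
| 0.4 | 0.2 | -0.21 to -0.07 | +0.33 to +0.38 | 0.37 |
| 0.4 | 0.4 | -0.01 to +0.12 | +0.24 to +0.32 | 0.37 |
| 0 | 0 | -0.26 to -0.11 | +0.04 to +0.12 | 0.00 |
| 0 | 0.4 | +0.14 to +0.28 | -0.13 to -0.05 | 0.00 |

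The partial R is 0.4/√1.16 = 0.37 with help and 0 without, whatever k, ρ and s are, as long as prior immunity acts only through the two measured baselines.

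**4. A second model as a cross-check.** Without A0 (dC = -b·C0 + e1, dA = g·dC + h·C0 + e2, s = 0.8) and with g = b = 0.5, h = 0: Var(dC) = 0.89 and Var(dA) = 0.2225 + 0.64 = 0.8625. Change R = 0.5 × 0.943/0.929 = +0.51. Baseline R = -0.25/0.929 = -0.27. Over b = 0 to 0.75 and h = -0.3 to +0.3, change R stays between +0.35 and +0.67, while baseline R runs from -0.60 to +0.32.

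**The case against.** The best defence is that the two sections do not contradict each other. Section 4.2.2 names its variables, windows and statistic, so it can be computed without 12.4. The correlation in 12.4 is openly a baseline question: it "will be used to study how baseline CD4 responses and/or memory B cell derived polyclonal antibodies, HAI, MN titers affect the boost responses". It is not offered as the analysis of the secondary outcome, and the regression, not that correlation, is the section's declared study of CD4 help. All of this stands. It means that 12.4 omits one listed outcome and adds a different analysis.

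A reader might go further and infer that the two sections are rival definitions of one outcome, so that following 12.4 would reverse the sign and be reported as CD4 cells failing to help. The documents do not support that. Nothing in 12.4 invites that reading of the baseline correlation, and the sign reversal needs an assumption that baseline CD4 has little direct effect of its own. Memory CD4 cells present before vaccination could plausibly help too, and with k = 0.4 the baseline correlation is close to zero or slightly positive.

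It can also be said that adjusting for Day 0 values introduces a quantity that 4.2.2 does not contain. That is correct, so the adjusted figure belongs beside the promised R and should not replace it.

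What the defence leaves open is the regression. Its CD4 predictor has no timepoint and baseline titre is not among its adjustments. Baseline control is mentioned in 12.4 only for the mixed-model comparison of groups over time.

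**Conclusion.** The point holds as an omission and an under-specification. The 4.2.2 correlation has no counterpart in 12.4. The boost in 12.4 is not tied to Day 14 or Day 28. The regression for CD4 help has no CD4 timepoint and no baseline-titre adjustment. These conclusions rest on the text alone, with one inference: that the 4.2.2 windows denote changes, by analogy with 4.2.1.

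The size is conditional. At an assumed help slope of 0.4, the change correlation stays positive (+0.24 to +0.45), while the baseline correlation runs from about -0.39 to +0.12. Opposite signs are possible, not established. Without help, the unadjusted change correlation can still lie between -0.13 and +0.12, whereas the version adjusted for both Day 0 values is 0.00. That advantage has a limit: if prior immunity drives both changes directly, simulations under similar assumptions left a partial R of 0.06 to 0.16 without any help.

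The outcome is secondary, 12.2 calls the study explorative, and no primary comparison is affected. The change should be made, but the trial does not depend on it.

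**What to change.** In section 12.4:

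1. Specify the 4.2.2 outcome: by vaccine arm, the correlation of log CD4 change (Day 14 minus Day 0) with log HAI or MN change (Day 28 minus Day 0). Name one coefficient, Pearson or Spearman, and the antigen pairings. State whether cohort means arm, or arm within year.
2. Beside it, report the partial correlation given Day 0 titre and Day 0 CD4.
3. In the regression of HAI/MN response on CD4 specificities, use the same Day 0 to 14 CD4 change as predictor, the same Day 0 to 28 antibody change as response, and the same Day 0 adjustment.
4. Keep the baseline-with-boost correlation, labelled as a separate question about prior immunity and not as the test of CD4 help.

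The cost is wording and slightly more analysis. All the samples are already scheduled. Adjustment reduces confounding by prior immunity but does not guarantee its removal, and the report should say so.
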